I am very grateful to all the departments of AUA, faculty members, staff at library, administrative staff, and [name] for their help and continuous support in all these three years.

Last but not the least my humble gratitude to my mother, my sister, my friends and Miss. [name] for their help, without them, I would have been incomplete.

Executive Summary

The goal of “Physician Leadership Development Program: a proposal for a pilot project” is to develop strong leadership skills among family physicians to play an effective physician-leader role for better healthcare services. Armenia needs skilled and motivated physician-leaders to address various challenges and issues across the healthcare system, from out-of-pocket payments, implementing healthcare as a fundamental human right, to patient-centered care. In order to overcome these challenges, health institutions need physicians equipped with leadership and managerial skills in all levels of administrative positions in the healthcare setting. Physician-leaders are expected to be inspired by a shared goal, to be caring and supportive, to be engaged in an open and effective communication with patients. The other two key characteristics of physician-leaders are responsiveness and trust building with the patients. One of the main indicators of measuring patient satisfaction is a patient-physician relationship.

We propose to implement a Physician Leadership Development Program for family physicians of Heratsi polyclinic, which is under the administration of Yerevan State Medical University. During the program, the core training personnel will consist of two physicians who have taken “training of trainers” course. The first session of the training will be the introduction to the program. The other twenty sessions will equally divide into four sessions for each of the domains: Demonstrating personal qualities, Working with others, Managing services, Improving services, and Setting direction.

Evaluation of the Physician Leadership Development Program consists of one baseline and two follow-up assessments of both intervention and comparison groups. The target population of the intervention group is the family physicians’ patients who have registered in the Heratsi polyclinic and attained treatment; whereas, in the comparison group the family physicians’ patients who have registered in the Muratsan Polyclinic and attained treatment. The estimated the sample size of the evaluation program should be 1,262 in each group.

The data collection will be done through a self-administered questionnaire. The study team developed a structured questionnaire, which includes 30 close-ended questions about socio-demographic characteristics and patient perspective of patient-physician relationship. The dependent variable of interest is Patient-Physician Relationship percent score, which is a numerical continuous outcome variable. The main independent variable of interest is being from Heratsi (intervention) or Muratsan (comparison) polyclinics. The control variables suggested by the literature include participant’s sex, age, socio-economic status, educational status, and marital status. After data collection, data entry and cleaning will be done.

Descriptive statistics will be done to describe the study participants. Followed by Chi Square test and T-test. Then, bivariate linear regression analysis and multivariate linear regression analysis will be made to control for the confounders. The estimated budget of the project is 6,007,800.00 AMD. The estimated budget for this grant proposal is calculated based on optimal fixed and overhead costs. The anticipated duration of the project is 14 months. Institutional Review Board (IRB) of the American University of Armenia approved the study protocol.

1. Overview

The project is a Community Service Grant Proposal for a “Physician Leadership Development Program” among family physicians. The goal of this proposal is to develop strong leadership skills among family physicians to play an effective physician-leader role for better healthcare services. This goal can be achieved by offering 21 sessions of Physician Leadership Development Program to family physicians working in.

1.1 Objectives of the project

By the end of the Physician Leadership Development training Program, the physician will:

- Develop an effective patient-physician relationship
- Deliver better quality health care
- Deliver effective and cost-efficient health care
- Build leadership competencies to drive change, manage teams, and provide effective healthcare

2.1 Introduction/Background

Armenia is a lower-middle income country and a part of the former Soviet Union. It is in a transitional stage of development after going through a great economic crisis after independence in 1991.¹ Armenia inherited Semashko health care system from the Soviet Union.¹

Armenia needs skilled and motivated physician-leaders to address various challenges and issues across the healthcare system, from out-of-pocket payments, implementing healthcare as a fundamental human right, to patient-centered care. The future physician leaders will need more than a medical degree to make a significant impact on the Armenian healthcare system and their local healthcare administrative settings.

At present, medical educational institutions in developed countries are undergoing a process of significant changes because of health reform and financial constraints. The main components of this process are changes in the curriculum in medical education and administrative proceedings in healthcare centers.² In order to overcome these challenges, health institutions need physicians equipped with leadership and managerial skills in all levels of administrative positions in the healthcare setting. This need requires the development of special programs aimed at developing physicians' leadership skills to enhance the patients' experience.²

“I suppose leadership at one time meant muscles;

But today it means getting along with people.”

--Mohandas Karamchand Gandhi.

According to the World Health Organization's (WHO) Quality of Care report, there are six domain of quality of intervention to help policy makers to address the quality of health. In the WHO's Quality of Care report, leadership is the first and the most important domain for the need analysis of the policy on health care, determination of health goals and quality inventions in the healthcare.^{3,4} In the present day, a healthcare system is an organization with huge complexity, facing new challenges every day.^{5,6} In order to handle this complexity, effective leadership needs to be integrated into the system at all levels.^{5,7} Studies show that quality initiatives fail to realize the desired outcomes if there is no strong or consistent leadership support.^{3,4} In order to overcome the resistance to the change for improving overall healthcare outcomes, sophisticated leadership are required. The latter is often in short supply.⁸ Healthcare institutions around the world are trying to reach universal health coverage and improve the efficiency of the system to better utilize scarce resources. In

this ongoing battle in the healthcare system, there is an urgency for strong leadership in healthcare.^{9,10}

So far, definitions of the leadership were versatile, and a few might apply for the healthcare system.¹¹ Warren Bennis, pioneering in the field of leadership studies, defines leadership “a function of knowing yourself, having a vision that is well communicated, building trust among colleagues, and taking effective action to realize your own leadership potential”.¹¹

2.2 Leadership in Healthcare

The very definition of leadership can confuse and derail efforts to engage physicians as healthcare leaders since the terms “leaders” and “leadership” are often confused.¹² Kumar (2013) suggests “leaders can truly be seen as change agents, placing the concern and development of others above themselves. This may be far more beneficial for health service improvement. Engaging professionals to buy into a vision and allowing them to lead the process of change is likely to be more successful than other approaches. Rather than toppling resistance to change, transformational leadership acknowledges and deals with it”.¹¹ Stogdill (1948) wrote “Leadership may be considered as the process (act) of influencing the activities of an organized group in its efforts towards goal setting and goal achievement”.¹³

Physician-leaders are expected to be inspired by a shared goal, to be caring and supportive, to be engaged in an open and effective communication with patients.^{11,14,15} The other two key characteristics of physician-leaders are responsiveness and trust building with the patients.^{4,16,17} Physicians trained in leadership can help to engage other professionals at different levels to embrace the organization’s mission and vision. They empower themselves to lead, execute team orientation and development in organizational culture through vision, enthusiasm, and passion. It is critical to march forward leadership in today’s healthcare system.^{11,18}

2.3 Leadership Development for Physicians

Physicians' engagement is a psychological state established through an interactive relationship with patients and working environment conditions in three frames: structural, political, and cultural. These frames can empower and depower them.¹⁹ Empowering physicians, attaining greater freedom, and enhanced accountability are innovative strategies to improve the quality of healthcare. However, these strategies are not sufficient to attain quality healthcare. Here comes the need for developing leadership for physicians.⁴ Leadership development programs among practitioner or physicians, nurses, and health care administrators have shown a significant change in the overall outcomes of the health care.^{3,4,10,18}

Physician leadership development programs have been created and implemented in many countries around the world. For instance, after a similar program, Jönköping County Council in Southern Sweden, showed 2-3 times better performance than all other Swedish peers on all health status outcome indicators.²⁰ This Council, where the CEO, the physician and board chair developed a good working relationship and transparency through open communication, good financial performance and thorough trust building where the board interference in day-to-day operations does not exist.²⁰

Another example of the importance of physician leadership development is from Denmark. Physicians in Denmark take a mandatory leadership course at the post-graduate level. Moreover, completion of leadership development program is a requirement for all medical directors on the boards of hospitals and heads of clinical departments. This requirement was enacted in order to more effectively address day-to-day administrative challenges observed in the healthcare system.^{20,21}

One of the world's best competency frameworks for physician leadership development was established by the Academy of Medical Colleges and National Health

Service (NHS), Institute for Innovation and Improvement, United Kingdom (UK).²⁰ Some authors suggested that NHS was the first system to adopt leadership development approach at all levels for its healthcare personnel in the world.²² This leadership development approach at all levels of the NHS provides Continuous Quality Improvement (CQI) and Total Quality Management (TQM) for the healthcare organizations.²² The NHS's "Leadership Academy" is committed to connecting better leadership to better patient care.²³ Besides committing for quality of patient care, programs at Leadership Academy, NHS, Leadership Academy's leadership development program is to create the culture that makes physicians and clinicians the ownership of the budgets, expenditure accountability and financial performance of service.²⁴

3. Methodology

3.1 Conceptual Framework

According to the World Health Organisation's (WHO) definition, health systems include "*all the activities whose primary purpose is to promote, restore or maintain health*".²⁵ The WHO's Conceptual framework suggests that the ultimate performance goals of health systems are "health", "fairness in financial contribution" and "responsiveness" (Appendix 1).²⁶ For this project, the basic assumption from the WHO framework suggests that investment in leadership trainings will improve the quality of healthcare and eventually improve responsiveness of provided care.

Responsiveness of health systems is defined as the client's legitimate expectation regarding the non-health dimension of the population's interaction with the health system.^{26,27} Responsiveness also contributes to the promoting utilization of the health system.²⁵ Responsiveness has two key components; those are "respect of persons" and "client orientation".²⁶

According to the WHO Quality of Care report, the leadership development programs have shown improvement in overall quality of care, client orientation, and in organizational behavior in the healthcare settings.³ As the literature shows, leadership development programs for physicians improve the overall responsiveness of the system and the patient-physician relationship.^{4,26-29}

“The Patient is the center of the medical universe,

Around which all our works revolve and towards which all effort tend.”

- John Benjamin Murphy

3.1.1 The Patient-Physician Relationship

One of the main indicators of measuring patient satisfaction is a patient-physician relationship.³⁰ The latter is an integral part of successful healthcare delivery.³¹ Although the concept of patient-physician relationship has not been clearly defined,³² it plays a great role serving as a “window mirror” model.³³ A window-mirror model for patient care and patient-physician relationship exists when there is mutuality of caring between patients and physicians, each respecting the other for their mutual benefit.³³ The patient-physician relationship is the most sensitive indicator of the persistence of difference and delivery of the care.^{3,30} A good relationship motivates physician to do well and the patient to cooperate better.³⁰ The person who seeks care can also be defined as “client” or “customer” rather than as a patient.³⁰ If the patient has a possibility of choosing the provider, the patient-physician relationship plays a critical role in the success among the competing providers. According to WHO’s Quality of Care report, engagement of patients and the population is a critical domain when building strategies for quality.³ The consumer or the patient is considered the center of the health care services,²⁵ and their first contact with healthcare is the physicians.^{3,25,30}

3.2 Implementation Plan Synopsis

3.2.1 Program

We proposed to implement the Physician Leadership Development Program to the family physicians of Heratsi polyclinic, which is under the administration of Yerevan State Medical University. During the program, the core training personnel will consist of two physicians who have taken “training of trainers” course. These physician trainers should have a Master of Public Health (MPH) degree from the American University of Armenia. The trainers will take the free online course “Edward Jenner Program” provided by Leadership Academy in National Health Services, United Kingdom.³⁴ The trainers will complete the course and obtain a certificate. On completion of the online program, the trainers will use these materials to teach the family physicians. The trainers will also translate the online program materials into Armenian. The training course includes topics not only about the leadership (as a core component), but also about cooperation, planning, resource management, innovation in patient care, assessment of outcomes of patient care and decision-making.

The program consists of 21 sessions (each 40 minutes), three sessions a week in a seven-week period. The physicians in the primary health centers work on two shifts; Morning shift: (9:00 AM -1:00 PM) and afternoon shift (1:00 PM - 5:00 PM) for six days a week. Each physician has his/her schedule on even and odd days of the week. Separate sessions will be offered to two cohorts on even and odd days of the week. The session will conduct on each day of the week from 2:00 PM until 3:30 PM with a break of fifteen minutes. No session will schedule for Sundays. The sessions will be conducted at the American University of Armenia.

3.2.2 Educational Materials

Educational materials include the copies of translated lectures from the Physician Leadership Development Program named “Edward Jenner Program” provided by Leadership Academy, National Health Services in United Kingdom³⁴ (Appendix 2).

The program covers five domains:

- 1) Demonstrating personal qualities
- 2) Working with others
- 3) Managing services
- 4) Improving services
- 5) Setting direction

The first session will be the introduction to the program. The other twenty sessions will equally divide into four sessions for each domain. The main curriculum guide of the program is included in Program Curriculum Guide.

3.3 Evaluation Plan Synopsis

Evaluation of the Physician Leadership Development Program is an important component of this grant proposal. The evaluation plan consists of one baseline and two follow-up assessments of the both intervention and comparison groups. These assessments are to assess the outcomes of the Physician Leadership Development Program of the proposed project. The evaluation is to quantify patients’ perspective of Patient-Physician Relationship through a quantitative method by the survey questionnaire.

3.3.1 Measurable Objectives

- A month after the end of the program (December, 2015), the Patient-Physician Relationship percent score of the physicians' patients will increase by 15% compared to the baseline percent score of the intervention group (August 2015).³⁵
- Six months after the first follow-up assessment (June 2016), the Patient-Physician Relationship percent score of the physicians' patients will increase by 17% compared to the baseline percent score of the intervention group (August 2015).³⁵
- Six months after the first follow-up assessment (June 2016), the Patient-Physician Relationship percent score of the physicians' patients of the intervention group will be higher by 10% compared to the comparison group.³⁵

3.3.2 Study Settings and Target Population

In the intervention group, the target population is the family physicians' patients who have registered in the Heratsi polyclinic and attained treatment. In the comparison group, the target population is the family physicians' patients who have registered in the Muratsan Polyclinic and attained treatment. Heratsi and Muratsan polyclinics are selected for convenience; they both are under the administration of Yerevan State Medical University. Moreover, the organizational culture, administrative proceedings, pay scale, budgeting, and management are similar to each other. The inclusion and exclusion criteria of the survey participants are (Table 1):

Inclusion Criteria:

- a) Being registered with Heratsi or Muratsan polyclinics
- b) Being eighteen year old to sixty-five years old
- c) Visiting family physicians

Exclusion Criteria:

- a) Being registered with these polyclinics after the baseline assessment (exclusively for follow-up assessments)
- b) Patients who participated in the previous assessments in this survey (exclusively for follow-up assessments)

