3.3.2 Evaluation Study Design

The evaluation will consist of one baseline assessment and two follow-up assessments. The baseline assessment (**O₀**) of Patient-Physician Relationship percent score of the family physicians' patients of Heratsi and Muratsan Polyclinics will be gathered in August 2015. The follow-up assessment will be done one-month after the training in December 2015 (**O₁**) and seven months after the completion the program (six month after the first follow-up) in June 2016 (**O₂**). A Quasi-experimental, non-equivalent Control Group Design with independent groups will be applied for the proposed evaluation. The chosen design allows us to have a comparison group.

Intervention Group	O₀	X	O₁	O₂
Comparison Group	O₀		O₁	O₂

O₀ - Baseline Data Collection

X – Intervention

O₁ – Follow-up assessment one month after the end of the intervention

O₂ – Follow-up assessment six months after the first follow-up assessment

Threats to Internal Validity: History threat to internal validity will not be a significant issue since programs on leadership for family physicians Armenia are rare; moreover, having a comparison group will address the issue. Maturation can be a threat because the leadership development might not be only due to the intervention (Physician Leadership Development Program) but it might be due to the natural process of the physician acquired some skills during their practice; however, having a comparison group helps to address the issue. Testing cannot be a threat because the survey participants are independent. Instrumentation cannot be a threat, as the questionnaire used for the baseline and two follow-up assessments will be the same. Regression to the mean cannot be a threat because the survey participants are not people with only outlying characteristics related to the outcome variable of interest.

Selection bias can be a threat because there is no randomization of the survey participants into intervention and comparison groups. Moreover, the survey participants in both groups might differ from each other in terms of demographic and severity of disease. Compensatory rivalry can be a threat because the program participants will be aware of the evaluation study. Therefore, the family physicians might change their behavior and be friendlier with their patients. Attrition cannot be a threat because of survey participants are independent groups.

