Response options have nine levels of agreement with each statement from “Strongly Disagree” to “Strongly Agree.” The patient-physician relationship score is the numerical continuous variable, which is a dependent variable. In the self-administered survey questionnaire, the socio-demographic questions refer to sex, age, marital status, socio-economic status, and educational status. The self-administered questionnaire will take about 10 minutes to complete and provides anonymity. To preserve the anonymity, no personal identification information will be collected. Instead, each questionnaire will have a special identification number. The special identification number will consist of six characters. The first character of the identification number will feature one English alphabet, i.e. “H” or “M”. Latter is to represent the polyclinic where the survey participant took the survey. The second character of the identification number will feature one Arabic number, i.e. “0” or “1” or “2”. The numbers “0” represent the baseline assessment and, “1” and “2” represent two follow-up assessments respectively. The other four characters of the identification number will feature Arabic numbers, which will be the numbers of the survey participant. For example, if

“H20604” is the special identification number on the questionnaire, then it implies that the survey participant is from Heratsi polyclinic, who took the survey in second follow-up assessment as 604th participant.

The self-administered survey questionnaire was translated from English into Armenian by two different certified translators and later both copies of the Armenian versions were compared, the most appropriate translated version was considered. The Armenian version of the questionnaire content consistency was reviewed by second year Masters of Public Health program’s students at AUA who are Armenian native speakers. The translated Armenian version of the self-administered survey questionnaire will be pretested among ten participants. The pretest will be conducted among the patients who visited family physicians in a selected polyclinic.

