3.3.4 Variables

The dependent variable of interest is Patient-Physician Relationship percent score, which is a numerical continuous outcome variable (Table 2). It is measured through 25 questions. The response options for each statement consists of nine levels of agreement between “Strongly Disagree” to “Strongly Agree”. The patient-physician relationship score ranging from 25-225 from the questionnaire will be re-calculated to patient-physician relationship percent score ranging from 11% to 100%.

The main independent variable of interest is being from Heratsi (intervention) or Muratsan (comparison) polyclinics. It is a nominal dichotomous type of variable. The special identification number of the questionnaire will identify the information.

The control variables suggested by literature include: participant’s sex, age, socio-economic status, educational status, and marital status.^{31,35,38,39} Literature shows that the above-mentioned control variables can influence the desired outcome of variable.^{31,35,38,39}

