Baseline Assessment (O₀) August 2015	
 a) Patients registered with Heratsi or Muratsan polyclinics b) Patients over the age of eighteen years old and under sixty five years old c) Patients visiting family physicians 	
Additional Criteria for the Follow-up Assessment (O₁) December 2015		
 a) Patients who registered with these polyclinics after August 2015 b) Patients who participated in the baseline assessment (O₀)
Additional Criteria for the Follow-up Assessment (O₂) June 2016		
 a) Patients who registered with these polyclinics after August 2015 b) Patients who participated in the baseline assessment (O₀) and the follow-up assessment (O₁)

Table 2: Variables and Sources of Data

Variables	Type	Measure	Sources
Dependent Variable Patient-Physician Relationship percent score	Numerical (Continuous)	Percent score (Minimum – 11% Maximum – 100%)	Self-administered questionnaire
Independent Variable Patients being from Intervention or Comparison polyclinics	Nominal (Dichotomous)	Patients of Family Physician from Heratsi or Muratsan	Self-administered questionnaire
Control Variables			
Age	Numeric (Continuous)	Age in Years	Self-administered questionnaire
Sex	Nominal (Dichotomous)	“Male” Or “Female.”	Self-administered questionnaire
Marital Status	Nominal	1) Single 2) Married 3) Widowed 4) Divorced	Self-administered questionnaire
Social-economic Status	Ordinal	1) Less than 50,000 drams 2) From 50,001 - 100,000 drams 3) From 100,001 - 200,000 drams 4) From 200,001 - 300,000 drams 5) Above 300,000 drams	Self-administered questionnaire
Educational Status	Ordinal	1) Incomplete secondary (less than 10 years) 2) School (10 years) 3) Professional technical (10-13) 4) Institute/University 5) Post-graduate	Self-administered questionnaire

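### Severity of disease is a named selection threat but is not recorded, and exclusions that apply only at follow-up can bias the two pre-post objectives

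*Protocol*

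**What the plan says.** **Severity.** Under threats to internal validity, Protocol 3.3.2 (Evaluation Study Design) says that there is no randomisation and that "the survey participants in both groups might differ from each other in terms of demographic and severity of disease". Section 3.3.4 and Table 2 list the control variables as "sex, age, socio-economic status, educational status, and marital status". The questionnaire in Appendix 3 has 25 relationship items and five socio-demographic items. None asks about health status, number of visits or length of registration.

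**Eligibility by wave.** Protocol 3.3.2 (Study Settings and Target Population) has two exclusions that apply only at O1 and O2: "Being registered with these polyclinics after the baseline assessment (exclusively for follow-up assessments" and "Patients who participated in the previous assessments in this survey (exclusively for follow-up assessments". Table 1 gives the first as "Patients who registered with these polyclinics after August 2015", with the same cut-off at both follow-ups. For the second, Table 1's O2 entry names patients who took part in O0 *and* O1. Both rules apply equally to Heratsi and Muratsan.

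**Sampling and forms.** Section 3.3.3.2 describes an exit survey that takes visitors at a fixed interval. Section 3.3.3 (Questionnaire) says that "no personal identification information will be collected".

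**Contrasts.** Objective 1 in 3.3.1 is that the score "will increase by 15% compared to the baseline percent score of the intervention group". Objective 2 has the same form, with 17%. Objective 3 is that the Heratsi score "will be higher by 10% compared to the comparison group" in June 2016. Section 3.3.3.1 also defines success as a difference between the groups at O1.

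**The concern.** There are two separate problems.

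1. **Between groups.** If one polyclinic's patients are sicker, and sicker patients rate the relationship differently, the O1 and O2 group differences carry that gap. The planned multivariate regression can adjust only for what is recorded, and an analysis plan written later cannot recover an item that was never asked.

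2. **Between waves.** In a visit-based sample, frequent attenders are the most likely to be taken at O0, and those taken are then barred. A fixed August 2015 registration cut-off also means that the shortest possible time registered grows from wave to wave. O0, O1 and O2 may therefore describe somewhat different patients. Objectives 1 and 2 have no comparison term, so any such drift enters them directly.

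**Working it through.** **1. Severity: the passages side by side.** Severity is named in 3.3.2 (Evaluation Study Design). It is absent from the controls in 3.3.4 and Table 2, and from Appendix 3. The bias in a group difference would be (difference between clinics in the share of sicker patients) x (score gap between sicker and other patients). The documents give neither factor. With an assumed 10-percentage-point difference and a gap of 1 to 5 points, it is 0.10 x 1 = 0.1 to 0.10 x 5 = 0.5 points, in either direction.

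**2. Time registered.** With the August 2015 cut-off, the minimum is 0 months at O0, about 4 at O1 (December 2015) and about 10 at O2 (June 2016). If 10% of baseline patients were recent registrants scoring 10 points lower (assumed), their absence later would raise the mean by 0.10 x 10 = 1 point.

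**3. Exclusion of earlier participants.** The protocol's expected gain is 64.07 - 55.71 = 8.36 points. All inputs below are assumed, except the 64 surveys a day and the divisor of nine in 3.3.3.2.

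- Fraction f of survey-hour visits sampled: 18% to 36%. At 64 surveys a day this means about 64/0.18 = 356 to 64/0.36 = 178 visits a day.
- 20% of patients make 4 visits per wave and 80% make 0.25. The frequent attenders' share of visits is (0.2 x 4)/(0.2 x 4 + 0.8 x 0.25) = 0.80.
- Frequent attenders score 5 points higher.
- P(taken in a wave) = 1 - (1 - f)^v. For v = 4 this is 1 - 0.82^4 = 0.55 and 1 - 0.64^4 = 0.83.
- Share at O1 = 0.8(1 - f)^4 / [0.8(1 - f)^4 + 0.2(1 - f)^0.25]. At O2 both exponents double.
- Change in mean = (share at follow-up - 0.80) x 5.

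| f | share at O1 | change at O1 | share at O2 | change at O2 |
|---|---|---|---|---|
| 18% | 0.655 | -0.7 | 0.475 | -1.6 |
| 36% | 0.429 | -1.9 | 0.123 | -3.4 |

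The result depends strongly on these inputs. If the frequent group makes 2 visits instead of 4, the O1 fall is 0.4 to 0.9; with 1 visit it is 0.2 to 0.4. Section 3.3.3.2 also divides the number of visitors by nine to get the interval. Nine a day for 20 days is 180 per wave, so f becomes 180/1262 of the values above, or 2.6% to 5.1%. The 4-visit model then gives falls of only 0.08 to 0.17 at O1 and 0.17 to 0.35 at O2. The conflict between 64 and nine a day is a separate matter.

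**4. Effect on a pre-post test.** With 1198 per wave, no programme effect and a 0.25-point shift, the standard error is SD x sqrt(2/1198). At the protocol's SD of 2.5 it is 0.102, and a two-sided 5% test is significant about 69% of the time. At an assumed SD of 10 or 15 this falls to 9% or 7%.

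**5. Comparison of changes.** Write e for the share of follow-up visitors excluded and D for how much higher they score than the others. The bias in the difference of changes is -(e in Heratsi - e in Muratsan) x D. With equal e it is 0. With e = 20% against 10% and D = 1 to 5 (assumed), it is 0.1 to 0.5 points in absolute size.

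**6. Table 1 at O2.** O0 participants are already barred from O1, so nobody can properly have taken part in both. Read literally, the O2 entry excludes no one. Section 3.3.2 bars anyone from the previous assessments, which means O0 or O1.

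**The case against.** The strongest reply is that the design already holds the answer: a comparison group measured at all three waves under identical rules. A shift common to both polyclinics cancels in a comparison of changes, and objective 3 and the success definition in 3.3.3.1 compare groups within one wave. This stands, but objectives 1 and 2 as worded do not use Muratsan, and a within-wave comparison is still open to unmeasured severity.

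Second, the registration cut-off is defensible: it confines every wave to people registered by baseline. That also stands. What remains is unequal time registered, and nothing in the documents shows whether this affects the score.

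Third, adjusting for self-rated health or visits at follow-up may remove part of a true effect if the programme changes them. This is fair, and it is why both sets of results should be shown.

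A reader might infer more than the documents support:

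- *That case-mix shift will be taken for programme effect.* The larger illustration lowers the follow-up mean and so works against the programme; the registration illustration works for it. The net sign is unknown.
- *That depletion must be stronger in the smaller clinic, so that a comparison of changes fails.* The protocol gives no visit volumes; they are to be obtained in July 2015.
- *That anonymity makes the exclusion unenforceable.* Staff approach each patient and can ask about earlier participation first. What is missing is any described step for doing so.
- *That the protocol treats severity as drifting between waves.* It names severity only as a difference between groups.
- *That the exclusion of earlier participants should be dropped.* The protocol relies on independent samples to dismiss testing and attrition threats and to use independent t-tests. Unlinked repeat respondents would undermine that.

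**Conclusion.** The point holds as a cheap and worthwhile improvement. From the text alone: severity of disease is a named threat that is not recorded, attendance and time registered are not recorded either, the two exclusions operate only at follow-up, and objectives 1 and 2 are uncontrolled pre-post contrasts. Group comparisons therefore cannot be adjusted for severity, and wave-to-wave case-mix *can* bias objectives 1 and 2.

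The size cannot be derived from the documents. Under the assumptions shown, the separate shifts run from under 0.1 to 3.4 points, with opposing signs, against a planned 8.36. The top of that range needs four survey-hour visits by frequent attenders within each 20-day wave and about 64 surveys a day. A shift equal in both clinics leaves a comparison of changes unbiased.

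**What to change.** Before the August 2015 baseline, and preferably before the questionnaire pretest planned for July 2015:

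1. Add short items on self-rated health or chronic illness, visits in the past 12 months and time registered, in both language versions. Update the stated count of 30 questions and Table 2.
2. Include these items as controls in the multivariate regression. Report results with and without them, because health rating and visits at follow-up could respond to the programme.
3. Reword objectives 1 and 2 so that Heratsi's change is judged against Muratsan's change over the same waves.
4. Keep the exclusion of earlier participants, and apply it through a screening question asked when staff approach the patient.
5. Reconcile Table 1's O2 entry with section 3.3.2, so that it covers participants in O0 or O1.

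The cost is a slightly longer questionnaire, one more question at approach, and reliance on self-report for health, visits, time registered and earlier participation. Baseline values not collected in August 2015 cannot be recovered later.
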